# C. Study Procedures and Measurements:

Participants may be pre-screened over the phone by the site or a market research firm to determine eligibility. A screening script will include a general review of key inclusion and exclusion criteria, the STOP-BANG questionnaire to assess the risk / possibility of an undiagnosed sleep disorder [46] and other questionnaires. Participants that meet all eligibility criteria will be asked to come into the office for a screening daytime visit (Visit 1) involving a detailed presentation of the study (informed consent) and an interview to verify eligibility and work schedules.

Participants who are interested and eligible will be consented. Participants will scheduled for a second daytime visit, 5 overnight lab visits, and provided with information on use of the actigraph. At Daytime Visit 2, participant qualification will be assessed based on the PowerSleep device data, actigraphy, and sleep logs. Qualifying participants will be randomized and scheduled for their sleep lab visits.

Participants will use the PowerSleep device within the active and sham study arm for two nights each week. After completing a baseline night in the lab, participants will sleep in the sleep lab two consecutive nights for two consecutive weeks. The first week participants will be randomized to active or sham and complete two consecutive nights. Participants will be asked to come in the same nights the following week to cross-over to the other arm of the study.

# Daytime Visit 1 Procedures (Up to 2 hours):

# Initial evaluation and anthropometric measurements:

Participants will be asked to report to the office for a daytime visit. After a full explanation of the consent and after all the participants' questions have been answered, they will be asked to sign the consent form. A detailed interview will be performed verifying eligibility criteria, and review of work and non-work schedules.

Participants will be asked to fill out the following baseline questionnaires:

- Medical History Questionnaire and Review of Systems
- Epworth Sleepiness Scale
- Insomnia Severity Questionnaire
- Cambridge-Hopkins Questionnaire (RLS screening)
- STOP-BANG Questionnaire
- Questions about sleep schedule and sleep quality.

Participants will have their height, weight, neck circumference, temperature, respiratory rate and blood pressure including heart rate (heart rate, systolic and diastolic after being seated for approximately 5 minutes) recorded.

Participants will be trained on the use of the sleep logs and actigraphy including instructions from the study staff on how to wear the actigraph. Participants will be asked to keep a sleep log and wear an actigraph during the entire course of the study. It is important participants keep to their regular sleep schedule throughout the study.

# Baseline Night (Sleep-Lab night 1):

Participants will be asked to come into the sleep-lab for a baseline night. This visit should occur as close as possible to Daytime Visit 2, preferably the night before the visit. If this cannot occur at that date due to the sleep lab or participant schedule this visit should be conducted at least 6 work days after the participant starts wearing the actigraph. Participants will be asked to come into the lab up to 4 hours before bedtime. Participants will be fitted with the PowerSleep device and PSG electrodes and asked to go to bed and awaken at the same time as their regular work-night sleep schedule. Participants will then be able to leave to complete their day. See Appendix I for standardized rules and restrictions for participant activities for the in lab study.

# Daytime Visit 2 Procedures (2 hours):

Participants will return to the office (within 2 weeks of daytime visit 1, ±2 days) with the actigraph and sleep diary for review by the study staff. Those participants who demonstrated alpha-delta waveforms as detected by the PowerSleep device during the baseline night will be excluded.

# Actigraphy review:

The sleep log and actigraph data will be reviewed by trained study staff prior to randomization to ensure participants continued eligibility.

Eligible participants will be randomly assigned to active or sham treatment during this visit in a 1:1 ratio. Participants and study staff will be blinded to the treatment they are receiving during each work week.

*Active treatment*: Participants will wear the PowerSleep device with soft audio tones (below 65dB to prevent arousals from sleep) administered via the speakers during deep sleep throughout the night.

*Sham treatment:* Participants wear the same PowerSleep device as with the active treatment, however no audio tones will be administered via the speakers.

Those participants that state they have heard tones during the baseline night will be set to a sensitive setting.

# Overnight in-lab visit 2 (Work Week 1)

Participants will be asked to come into the sleep lab during their work week on a Tuesday – Thursday night to complete their first study arm night. Participants will be asked to report to the lab up to 4 hours before bedtime with all study materials. Women of child-bearing potential will be asked to take a urine-pregnancy test. Prior to bedtime participants will go through a learning activity of the assessments they will complete the following night in order to have an understanding of the tasks. Participants will be fitted with the PowerSleep device, PSG electrodes and asked to go to bed and awaken at the same time as their regular work-night sleep schedule. Participants will complete the KSS, Samn Perelli, and VAS Sleep Quality 60 minutes of waking. After completing the questionnaires participants will be able to go to work, but will be instructed to not nap during the day. They will return to the sleep lab that evening 3 hours before bedtime.

### Overnight in-lab visit 3 (Work Week 1) followed by Daytime in-lab testing (8

**hours)**: On the next evening participants will be asked to return to the sleep lab for the second study arm night. Participants will be asked to report to the lab up to 4 hours before bedtime. Participant will be asked to complete the PAL learning activity prior to bedtime (120 to 30 minutes before lights out). Participants will be asked to go to bed and awaken at the same time as their regular work-night sleep schedule. Participants will be asked to wear the PowerSleep device and PSG electrodes during this overnight visit.

On the morning of the day following the overnight in lab visit work week 1, participants will remain in the lab and undergo the following assessments:

After Wake-Up

• Collect and download PowerSleep device data

Anytime after wake-up

- Review of any reported changes in medical condition since last visit
- Collect sleep logs
- Data download from actigraph
- Questionnaire identifying whether participant believes they had undergone active versus sham treatment
- Breakfast- participants can have one (1) 6 ounce cup of coffee or caffeine equivalent. Coffee or equivalent is only for those who routinely drink caffeine in the morning.
- Lunch

1 hour after wake up:

- Complete morning recall of PAL task
- Complete 3 minute PVT
- VAS for sleep quality
- Verbal fluency

- Karolinska Sleepiness Scale
- Samn-Perelli Fatigue Scale

2 hours after wake up:

- 4- Research Multiple Sleep Latency Test (see Appendix II for standardized MSLT procedures) each nap is followed by the following assessments:
  - Complete a 3 minute PVT
  - VAS for mood and vigor
  - Karolinska Sleepiness Scale
  - o Samn-Perelli Fatigue Scale
- •

Participants will continue to wear the actigraph and complete sleep logs until the next set of overnight visits.

# Overnight in-lab visit 4 (Work Week 2)

Participants will be asked to come into the sleep lab during their second work week on a Tuesday – Thursday night to complete the cross-over week portion of the study. Participants will be asked to report to the lab up to 4 hours before bedtime with all study materials. Women of child-bearing potential will be asked to take a urine-pregnancy test. Participants will be fitted with the PowerSleep device, PSG electrodes and asked to go to bed and awaken at the same time as their regular work-night sleep schedule. Participants will complete the KSS, Samn Perelli, and VAS Sleep Quality 60 minutes of waking. After completing the questionnaires participants will be able to go to work, but will be instructed to not nap during the day. They will return to the sleep lab that evening 3 hours before bedtime.

#### Overnight in-lab visit 5 (Work Week 2) followed by Daytime in-lab testing (8 hours)

On the next evening participants will be asked to return to the sleep lab for the second study arm night. Participants will be asked to report to the lab up to 4 hours before bedtime. Participant will be asked to complete the PAL learning activity prior to bedtime (120 to 30 minutes before lights out). Participants will be asked to go to bed and awaken at the same time as their regular work-night sleep schedule. Participants will be asked to wear the PowerSleep device and PSG electrodes during this overnight visit.

After Wake-Up

Collect and download PowerSleep device data

Anytime after wake-up

- Review of any reported changes in medical condition since last visit
- Collect sleep logs

- Data download from actigraph
- Questionnaire identifying whether participant believes they had undergone active versus sham treatment
- Breakfast- participants can have one (1) 6 ounce cup of coffee or caffeine equivalent. Coffee or equivalent is only for those who routinely drink caffeine in the morning.
- Lunch

1 hour after wake up:

- Complete morning recall of PAL task
- Complete 3 minute PVT
- VAS for sleep quality
- Verbal fluency
- Karolinska Sleepiness Scale
- Samn-Perelli Fatigue Scale

2 hours after wake up:

- 4- Research Multiple Sleep Latency Test (see Appendix II for standardized MSLT procedures) each nap is followed by the following assessments:
  - o Complete a 3 minute PVT
  - $\circ$   $\,$  VAS for mood and vigor
  - o Karolinska Sleepiness Scale
  - o Samn-Perelli Fatigue Scale

#### Exit Interview

Participants may be asked to complete an exit interview. During the interview, the participant will be asked to answer a set of questions about their opinions related to future iterations of the device, device functions, and technology preferences. This interview will be conducted by a member of the study staff or study sponsor. The interview may occur at the end of the study or as a phone interview. The interview will require up to an hour of the participant's time. Participants will be asked to indicate their approval to have the interview audio recorded and the potential to be contacted for future discussions.

# D. Temporary Discontinuation Criteria

If a participant develops a cold, flu or upper respiratory infection during the course of the work week, they may be asked to temporarily discontinue the study for one week. Participants will be instructed as part of the Informed Consent to call the study team if they develop a cold, flu or upper respiratory infection. The study team will let the participant know whether or not they can temporarily exit the study and restart at a later date or if they will need will need to discontinue the study.

# E. Outcome Measurements

#### Performance of PowerSleep device components:

- EEG signal quality as measured by impedance and ability to detect sleep-specific activity and/or events.
- Sleep staging algorithm performance as measured by sensitivity and specificity, PPV compared to the gold standard scoring.
- Audio stimulation algorithm performance as measured by the number and timing of tones provided.

**Slow Wave Activity:** EEG as recorded by the PowerSleep device and overnight PSGs will be analyzed for slow wave activity.

**Sleep Quality:** EEG from device downloads will be scored by an experienced registered polysomnographic technologist following current guidelines to determine sleep stage distribution. Sleep quality will also be measured via the Samn-Perelli Fatigue Checklist, the Karolinska Sleepiness Scale (KSS), and the visual analog scales.

Psychomotor Vigilance Testing – Brief (PVT – B): The Psychomotor Vigilance Task is a sustained-attention, reaction-time task that measures the speed with which participants respond to a visual stimulus. Sleep loss induces reliable changes in PVT performance, causing an overall slowing of response times, a steady increase in the number of errors of omission (i.e., lapses of attention, usually defined as response times ≥ 500 ms), and a more modest increase in the number of errors of commission (i.e., responses without a stimulus, or false starts) [47, 48]. Typically the PVT is a 10 minute assessment but a shorter 3 minute version (PVT-B) has recently been validated in controlled laboratory studies on total and partial sleep deprivation [47]. The PVT results will be assessed for average reaction time, average speed, number of omission errors, number of commission errors, and total number of errors.

**Verbal Fluency:** Participants are required to generate as many words directly related to the instructions as they can. This task has three conditions, the letter fluency condition (that has 3 trials), the category fluency condition and the switching condition. For each trial within each condition, the trial lasts for 60 seconds. This task is expected to take 6 minutes and will be audio recorded for scoring purposes.

**Paired associates learning task (PAL):** The Paired Associates Learning Task is a well-established cognitive task used to assess declarative memory. Participants are presented with word pairs to learn. Immediately following and again in the morning after they wake up they are tested on the recall of the words. The recall testing involves showing participants one word and they are asked to state the paired word that they

RESPIRONICS

learned previously. Overnight memory retention is determined by the difference in the number of recalled words between morning retrieval testing after sleep and immediate recall performance at learning before sleep. The testing is scored by a technician and may also be recorded for scoring confirmation.

**Karolinska Sleepiness Scale:** The Karolinska Sleepiness Scale (KSS) measures subjective levels of fatigue. KSS queries subjects as to how sleepy they feel at that moment. The subjects answer is based on a 9-point scale where 1 = extremely awake and 9 = extremely sleepy/fighting to stay wake. The KSS will be administered.[49, 50]

**Samn-Perelli 7-pt scale:** The Samn-Perelli is a 7 point scale which measures subjective levels of alertness. This scale ranges from fully alert, wide awake to completed exhausted, unable to function effectively. [51]

**Visual analog scales for mood & vigor:** Subjective alertness will be assessed using the Visual Analog Scale for Global Vigor and Mood, which combines the scores on four 10-cm scales (alert, sleepy, weary, and effort) to obtain a Global Vigor score between 0 and 40 cm and the scores on four 10-cm scales (happy, sad, calm, tense) to obtain a Global Mood score between 0 and 40 cm. Data are then divided by 4 to obtain a rating between 0-10. [52]

**Visual analog scale for sleep quality:** Sleep quality will be assess using the Visual Analog Scale for Sleep Quality, which combines the scores on four 10-cm scales (refreshed, alert, sleep quality, and deep sleep) to obtain a Global Sleep Quality score between 0 and 40 cm. Data are then divided by 4 to obtain a rating between 0-10. [53]

# Multiple Sleep Latency Test (MSLT)

The MSLT is the gold standard to evaluate physiological sleepiness and consists of a series of five nap opportunities presented at 2-h intervals beginning approximately 2 hours after initial (morning) awakening. We will use a modified version of the test, with four instead of five naps. [54, 55] The MSLT will be scored by an experienced registered polysomnographic technologist following the study protocol design.

**Polysomnography:** Both the active and sham PowerSleep devices perform online polysomnography. For each night of each treatment period, the recordings will be visually scored in 30-second epochs as wake, rapid eye movement (REM) sleep, or non-REM sleep stages N1, N2, and N3 according to standardized criteria. The following summary variables will be calculated: sleep period time (i.e. time interval separating sleep onset from morning awakening), total sleep time (i.e. SP – duration of intrasleep wake periods), sleep efficiency (i.e. total sleep time / time in bed \*100), duration of REM sleep, duration of light non-REM sleep (i.e. stages N1+N2), and duration of deep non-REM sleep (i.e. stage N3).

# F. Other Measurements

### STOP-BANG Questionnaire

This is an 8 item questionnaire which determines the risk for sleep apnea. These are a series of yes no questions. [46]

### Cambridge-Hopkins Screening questionnaire (for RLS)

This is a 2 to 13 question questionnaire. If participants answer yes to one or both of the first two questions then they answer a series of questions about sensations in their lower body. Depending on the responses participants may be found to be ineligible to continue.

### **Epworth Sleepiness Scale (ESS)**

This is an 8 item questionnaire that measures the general level of daytime sleepiness. Participants will be asked what the chance is they would doze off or fall asleep during different routine daytime situations.[56]

#### Insomnia Severity Questionnaire

The Insomnia Severity Index has seven questions about sleep problems. The answers are scored 0 to 4 and added to obtain a total score which indicates the clinical significance of the insomnia complaint. Total score can range from 0 (no clinically significant) to 28 (clinical insomnia, severe). [57]

# IV. ADVERSE EVENTS

An adverse event (AE) is any unfavorable and unintended sign, symptom, or disease temporally associated with the use of study device, whether or not considered related to study device.

AEs will include:

- Changes in the general condition of the participant
- Subjective symptoms offered by or elicited from the participant;
- Signs observed by the investigator or study personnel;

All concurrent disease including any change in severity or frequency of pre-existing disease.

A serious AE is one that:

- Results in death
- Is an immediate threat to life
- Results in permanent disability

Confidential

In addition, a serious AE is one that is judged by the investigator to be an important or medically significant event. Causality assessments of AEs: For all AEs, the investigator will provide an assessment of causal relationship to study device. Appropriate forms will be used for this purpose and filed in the case report forms and submitted to the IRB for review. They will be classified as related, possibly related, and not related. The severity will be adjudged as being mild, moderate, or severe.

# Adverse Event Follow-up

Participants with non-serious adverse events that are ongoing at the participant's last study visit must be followed until resolution or for 30 days after the participant's last study visit, whichever comes first. Non-serious adverse events that are reported during the 7 days following the participant's last study visit need to be recorded on the Adverse Events Case Report Form provided by the Sponsor and followed until resolution or for up to the 30 days after the participant's last study visit, whichever comes first. Serious adverse events will be followed until the event resolves or the event or sequelae stabilize. Serious adverse events that are reported on the Adverse Events Case Report Form provided on the Adverse Events Case Report or sequelae stabilize. Serious adverse events that are reported within 30 days of the participant's last study visit should be reported on the Adverse Events Case Report Form provided by the Sponsor.

### **Adverse Event Reporting Period**

Adverse events, both serious and non-serious, are to be recorded on the Adverse Events Case Report Form provided by the Sponsor from the time of the participant's informed consent signature until the end of the participant's study participation. If the participant reports or the Investigator learns of a new AE(s) up to 7 days after the participant's last study visit or a new SAE(s) up to 30 days after the participant's last study visit, the event needs to be recorded on the form provided by the Sponsor. All SAEs should be reported to the Sponsor within 24 hours of occurrence. All device deficiencies, use or user errors, and equipment failures will be documented. Use or User errors will be captured as part of the source documentation. Device deficiencies and equipment failures will be kept on a separate log. The serial numbers and type of deficiency/failure will be captured. Philips Respironics Engineering team will be notified to troubleshoot any issues associated with the PowerSleep Device.

# V. STATISTICAL ANALYSIS

Data quality will be assessed by the blinded personnel scoring the PSGs and device data. Criteria will be defined regarding whether the data sets are scorable and of sufficient duration to be included in the statistical analysis. These criteria will be consistently applied across all participant records and described in any study publications or reports.

# **Determination of Sample Size**

100 participants may be screened, up to 75 participants will be enrolled (randomized) in order to ensure at least 50 complete data sets. An interim analysis (N=9) from an international study of similar design suggests that between 24-47 participants would be required to reach statistical significance for the primary endpoint of slow-wave activity (SWA).

#### **General Considerations**

The primary analysis will include all completed participants who contributed at least one night of usable PSG data for each therapy condition. If there are participants whose therapy order is switched from their randomized assignment, then the results will be analyzed according to both the as-randomized and the as-treated assignments. If the sleep data are not usable for both nights in a given therapy, those participants will be excluded from the primary analysis, and site(s) may over-enroll to compensate for these missing data. The safety analysis will include all randomized subjects.

All variables will be summarized by descriptive statistics. The statistics for continuous variables include mean, median, standard deviation, minimum, maximum, 95% confidence interval (CI) for the mean, and number of observations. For categorical variables, frequencies and percentages will be presented. All analyses will be conducted using either SAS® or SPSS® software.

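### The safety set is defined by randomisation, but the device is worn for a full night before randomisation, so some exposed participants can fall outside it

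*Combined protocol and SAP*

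**What the plan says.** The safety population is given in one sentence of the Statistical Analysis part, under General Considerations: "The safety analysis will include all randomized subjects". The Safety Analysis section promises adverse event listings and names no population for them.

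The procedures in section III.C run in this order:

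- **Baseline night.** "Participants will be fitted with the PowerSleep device and PSG electrodes and asked to go to bed".
- **Qualification.** "At Daytime Visit 2, participant qualification will be assessed based on the PowerSleep device data, actigraphy, and sleep logs". Under Daytime Visit 2 Procedures: "Those participants who demonstrated alpha-delta waveforms as detected by the PowerSleep device during the baseline night will be excluded".
- **Further eligibility check.** At the same visit, and still ahead of randomisation, staff go through each person's actigraphy and sleep log to confirm that they qualify.
- **Randomisation.** "Eligible participants will be randomly assigned to active or sham treatment during this visit in a 1:1 ratio".

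Section IV defines an adverse event by its timing relative to device use, without reference to randomisation. The Adverse Event Reporting Period starts at signature of the consent form.

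**The concern.** A safety set of all randomised subjects works well when first exposure comes after randomisation. Here the first planned night in the device comes before it. One exclusion, alpha-delta waveforms, can be established only from a recording made with the device in place. The design therefore has its own route to participants who wore the device and were never randomised, and the stated safety set leaves them out.

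At stake is agreement between the definition of an adverse event (device use) and the population in which events are analysed (randomisation). A first-night skin reaction or pressure complaint in someone who then left the study would be recorded, but that person would not belong to the safety population. Any percentage of participants with an event, if produced under the general rule that categorical variables are summarised by frequency and percentage, would count neither that person nor the event.

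Two groups are not part of this point. Participants who are later randomised are already in the set, baseline-night events included. Participants who fail at Daytime Visit 1 without the device being placed on them have no exposure.

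**Working it through.** The plan gives no figure to reproduce, so the check has two parts: the order of events, then a scale under stated assumptions.

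**Order of events.** Consent is at Daytime Visit 1, so event recording is already running on the baseline night. The baseline-night section prefers the night before Daytime Visit 2 and allows some flexibility. Because qualification at that visit uses the device data from the baseline night, the night has to come first. Only those still eligible are then randomised. The sequence is consent, device wear, qualification, randomisation. No other section sets out a safety population based on exposure.

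**Scale.** Inputs:

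- k = number who wore the device and were not randomised. The documents do not give it. Assumed values are 0, 5 and 10.
- N = number randomised. The values 75 and 50 are used. In Determination of Sample Size, 75 is the upper limit for randomisation and 50 is the target for complete data sets, so N = 50 is an assumption.
- Nights per person. Section III.C schedules "a second daytime visit, 5 overnight lab visits". Each randomised participant is assumed to wear the device on all five nights and each non-randomised wearer on one.

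Formulas:

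- Share of wearers outside the set = k / (N + k)
- Share of device-nights outside the set = k / (5N + k)
- Mean nights per person if all wearers are included = (5N + k) / (N + k)

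| N | k | Wearers outside | Device-nights outside | Mean nights per person |
|---|---|---|---|---|
| 75 or 50 | 0 | 0% | 0% | 5.0 |
| 75 | 5 | 5/80 = 6.3% | 5/380 = 1.3% | 380/80 = 4.75 |
| 75 | 10 | 10/85 = 11.8% | 10/385 = 2.6% | 385/85 = 4.53 |
| 50 | 5 | 5/55 = 9.1% | 5/255 = 2.0% | 255/55 = 4.64 |
| 50 | 10 | 10/60 = 16.7% | 10/260 = 3.8% | 260/60 = 4.33 |

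The share of wearers is also the share of baseline-night exposures. No adverse event rate is assumed, because the documents give none.

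**The case against.** The strongest reply is that little depends on this sentence.

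- **Output.** The Safety Analysis section promises only listings, with no population limit. No event rate and no between-condition comparison of events is planned there. This stands: a frequency would arise only from the general descriptive rule.
- **Capture.** Events are recorded from consent, the investigator assesses causality for each one, and serious events go to the sponsor within 24 hours. This stands too. A reader might infer that baseline-night safety data are lost, but the documents do not support that. Only membership of the analysis set is at issue.
- **Disposition.** Subject Disposition, Treatment Compliance and Withdrawal Criteria already require discontinuations to be documented, with reasons where treatment or assessments stopped. Largely accepted. The sample-size section treats enrolled and randomised as the same thing, so a count of non-randomised wearers is not assured, but the information will exist.
- **Risk.** Section VI calls overall risks minimal and ties the skin effects mainly to the scrub and tape used for the PSG electrodes. Accepted. Headband pressure and the untested tether material do belong to the device, but nothing suggests a serious hazard from one night.

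Three stronger readings are tempting and go too far. The first is that up to 100 − 75 = 25 people are omitted. That difference is not a bound: 75 is itself a maximum, sites may over-enrol, and some of those screened fail before any device wear. The second is that event frequencies would be understated. The direction is unknown, because a one-night exposure pulls a per-person frequency down while withdrawal after a first-night event pushes it up, and the documents do not show that such withdrawals occur. The third is that the omitted participants received tones. The Actigraphy review text says "Those participants that state they have heard tones during the baseline night will be set to a sensitive setting", but the baseline-night section does not say whether tones are delivered. Those two passages need to be reconciled.

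None of this explains why a set meant to describe device safety should exclude people who slept in the device.

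**Conclusion.** The point holds and is minor. The stated safety set leaves out participants who wore the device on the baseline night and were not then randomised, although adverse events are defined by device use and collected from consent.

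The number affected is unknown and may be zero. On the assumed values k = 5 or 10 and N = 50 or 75, with five nights for each randomised participant and one for each non-randomised wearer, the omission is 6.3% to 16.7% of wearers and 1.3% to 3.8% of device-nights. No effect on any reported event rate can be shown from the documents. The efficacy analysis and the active-versus-sham comparison are not touched. This is a cheap improvement.

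**What to change.** - **General Considerations:** define the safety set as all participants on whom the PowerSleep device was placed at least once, including an attempted fitting. The attempted fitting needs naming because failure to achieve a suitable headband fit is an exclusion criterion and no section says when fit is checked.
- **Safety Analysis:** state that the listings cover all consented participants, so that events recorded from consent in people never fitted are not dropped. State that any event frequencies use the device-exposed set, and that baseline-night events in non-randomised wearers are shown separately because their exposure is one night.
- **Between-condition comparison:** keep randomised subjects for any active-versus-sham comparison of adverse events.
- **Optional:** add a disposition count of participants who wore the device and were not randomised.

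The cost is one revised sentence under General Considerations and a short addition to Safety Analysis. No new data, visits or procedures are needed. The only downside is that a reported event frequency may shift slightly, in either direction.
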